4.1.7 Dose limiting toxicities

DLTs will be recorded throughout the trial, and should be reported to the sponsor (AESIs, see Section [5.2.9.1.4](#)) within 24 hours of first knowledge.

Any of the following AEs will be reported as potential DLTs, and will be classified as DLTs following review by the Investigators and the sponsor, unless unequivocally due to underlying malignancy or an extraneous cause.

DLTs observed during the MTD evaluation period will be considered for MTD determination. However, all AEs and SAEs meeting criteria of DLT observed in all treatment cycles will be considered for determining a Recommended Phase 2 Dose (RP2D)

Haematologic toxicities:

- Any Grade 5 toxicity
- Neutropenia Grade 4 lasting for >7 days
- Grade ≥ 3 documented infection with neutropenia
- Febrile neutropenia (absolute neutrophil count $<1.0 \times 10^9$ cells/L and fever $\geq 38.5^\circ\text{C}$ or a sustained temperature of $\geq 38.0^\circ\text{C}$ for more than 1 hour)
- Grade 4 thrombocytopenia, or Grade 3 thrombocytopenia with bleeding
- Thrombocytopenia of any Grade which requires platelet transfusions
- Grade 4 anaemia unexplained by underlying disease
- Anaemia of any Grade which requires blood transfusions

Non-haematological toxicities:

- AST or ALT >3 times ULN and concurrent total bilirubin >2 times ULN without initial findings of cholestasis
- \geq Grade 4 AST or ALT of any duration
- Any \geq Grade 3 non-haematologic toxicity with the following exceptions:
 - Grade 3 irAE that resolves to \leq Grade 1 or to baseline with immunosuppressive therapy within 2 weeks
 - Grade 3 fatigue that persists <7 days
 - Grade 3 rash that resolves to \leq Grade 1 within 2 weeks
 - Grade 3 or 4 elevation in serum amylase and/or lipase that is not associated with clinical or radiographic evidence of pancreatitis
 - Grade 3 electrolyte abnormality that lasts <72 hours, is not clinically complicated, and resolves spontaneously or responds to conventional medical intervention
 - Grade 3 nausea or vomiting that lasts <48 hours, and resolves to \leq Grade 1 either spontaneously or with conventional medical intervention
 - Alopecia
 - Grade 3 asymptomatic endocrine disorders (thyroid, pituitary, and/or adrenal insufficiency) that are sufficiently managed with or without systemic corticosteroid therapy and/or hormone replacement therapy.
 - Grade 3 tumour flare
- Any Grade 4 or 5 AE other than disease progression
- Any Grade 2 pneumonitis of any duration
- Any Grade 2 uveitis, eye pain, or blurred vision that does not respond to topical therapy and does not improve to Grade 1 severity within 2 weeks or requires systemic treatment
- Any \geq Grade 2 toxicity that persists and results in > 14 days delay of administration of study medication (BI 836880 in Part I, BI 836880 and BI 754091 in Part II) on Cycle 2 Day 1
- Hypertension: systolic blood pressure \geq 160 mm Hg or diastolic blood pressure \geq 100 mm Hg, confirmed by second measurement of an additional set of 3 BP measurements, or 3 sequential ambulatory blood pressure measurements when indicated (e.g. white coat effect), which cannot be controlled by hypertensive medication and requires a dose reduction/discontinuation of trial medication(s). Refer to Section [10.3](#) for details of the assessment of blood pressure
- Grade \geq 3 proteinuria (urinary protein \geq 3.5 g/day). Refer to Section [5.2.4.4](#) for the assessment of proteinuria

NOTE: Any laboratory abnormality which is considered not clinically relevant by the investigator or resolves spontaneously, or resolves with appropriate treatment is not a DLT. Clinically relevant abnormalities must be documented as AEs.

Late immune-related DLTs are irAEs that meet the same grading criteria as DLT criteria, but occur after Cycle 1 administration during Part 1. These, as well as all toxicities will be monitored throughout the trial. If any late immune-related DLT is reported during dose-escalation, the BLRM will be rerun including the late immune-related DLT, and updated results will be reviewed in the SMC meeting to recommend the next dose level and cohort size.

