1.4.2 Risks

Both BI 836880 and BI 754091 are investigational agents. [Table 1.4.2: 1](#) displays the anticipated side effects of the study drugs, based on the mechanism of action, observed clinical data from ongoing studies, and published clinical data for drugs targeting VEGF, Ang2, and PD-1.

Table 1.4.2: 1 Potential risks, their rationale, and mitigation strategy

Potential risks of clinical relevance for this trial	Summary of data, rationale for the risk	Mitigation strategy
Investigational Medicinal Product BI 836880 (monotherapy)		
Hypertension	This is a class effect and has been identified as an expected AE in this trial. In Phase I trials, Grade 1 or 2 hypertension has occurred in 31.0% of patients and Grade 3 hypertension in 27.6% of patients. All hypertensive	Patients with uncontrolled hypertension are excluded. Frequent blood pressure monitoring is implemented.

Proprietary confidential information © 2019 Boehringer Ingelheim International GmbH or one or more of its affiliated companies

	episodes were transient requiring no treatment or resolved with the initiation or intensification of anti-hypertensive agents.	
Thromboembolic events (e.g. pulmonary embolism, deep vein thrombosis)	This is a class effect and expected AE with antiangiogenics.	Patients with history of severe thromboembolic event in the past 12 months are excluded.
Bleeding	This is a class effect and expected AE with antiangiogenics.	Patients with history of severe haemorrhagic event in the past 12 months are excluded. Full-dose anticoagulation (according to local guidelines) with Vitamin K antagonist and other anticoagulation are not allowed during the trial conduct.
Infusion related reactions	As with any mAb, allergic reactions to study medication administration is possible and they are potentially severe.	Patients with history of severe hypersensitivity reactions to other mAbs are excluded. A 48-hour hospitalisation with access to intensive care is mandated for all patients after the first study drug administration to secure the patient safety.
Drug-induced liver injury (DILI)	Rare but can be a potentially severe event, thus under constant surveillance by sponsors and regulators for all drugs in development.	Timely detection, evaluation, and follow-up of laboratory alterations in selected liver laboratory parameters to ensure patients' safety.
Investigational Medicinal Product BI 754091 (monotherapy)		

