5.2.4 Safety laboratory parameters

Blood and urine samples for assessment of general safety laboratory examinations have to be collected at the time points specified in the [Flow Chart](#), and will be analysed by the site's local safety laboratories. The laboratory tests should be more frequent in case of relevant findings, e.g. in case of grade 4 neutropenia, which will be counted as DLT if not recovered within 7 days, or proteinuria, for which determination of CTCAE grade 2 or grade 3 need to be done by quantitative measurement, or grade 3 electrolyte abnormality, which will be counted as DLT if not recovered within 72 hours (see Section [4.1.7](#)). Screening laboratory assessments performed within 72 hours of the first trial treatment administration are not required to be repeated on Cycle 1 Day 1. In cases where screening laboratory investigations have been performed >72 hours prior to the first trial treatment administration, the results of the new laboratory investigations performed within 72 hours of the first trial treatment administration must be available to confirm eligibility.

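### Protocol 4.1.7 contradicts itself on controlled Grade 3 hypertension and on laboratory criteria once the value recovers, and both feed the primary DLT count

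*Protocol*

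**What the plan says.** The number of patients with DLTs in cycle 1 is a primary endpoint in both parts (Protocol 2.1.2) and is what the trial feeds into the BLRM. SAP 5.1 and 7.4 refer to Protocol 4.1.7 for the definition and add no rule of their own.

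Section 4.1.7 is an any-of list: meeting one criterion makes an event a potential DLT. Investigators and sponsor then review it, and the only stated grounds for not classifying it as a DLT are underlying malignancy or an extraneous cause.

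- General clause: any event at or above "Grade 3 non-haematologic toxicity with the following exceptions". Nine exceptions follow, and none is hypertension.
- Hypertension criterion: a confirmed reading of at least 160 mm Hg systolic or 100 mm Hg diastolic, "which cannot be controlled by hypertensive medication and requires a dose reduction/discontinuation of trial medication(s".
- Among the other criteria: "Grade 4 AST or ALT of any duration" (Grade 4 or higher), and "Any Grade 4 or 5 AE other than disease progression".
- Closing NOTE: "Any laboratory abnormality which is considered not clinically relevant by the investigator or resolves spontaneously, or resolves with appropriate treatment is not a DLT".

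Section 5.2.4 restates two laboratory rules: "grade 4 neutropenia, which will be counted as DLT if not recovered within 7 days" and "grade 3 electrolyte abnormality, which will be counted as DLT if not recovered within 72 hours".

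**The concern.** Two investigators who follow 4.1.7 faithfully can classify the same patient differently, and nothing in the protocol or SAP says who is right.

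The hypertension case is not remote. Table 1.4.2:1 reports that "Grade 1 or 2 hypertension has occurred in 31.0% of patients and Grade 3 hypertension in 27.6% of patients" in earlier Phase I use, and that all episodes were transient or resolved with antihypertensive treatment. The controlled episode is therefore the usual one. Hypertension and proteinuria were each part of a DLT in two patients of the weekly trial 1336-0006 (Protocol 1.4.3).

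The classification has consequences beyond the count. A DLT forces a treatment hold and, from 720 or 360 mg, a lower BI 836880 dose on resumption (4.1.6). The BLRM is also to be re-run with DLTs from all cycles when the RP2D is chosen (5.2).

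**Working it through.** **Hypertension.** Take a patient with confirmed Grade 3 hypertension in cycle 1 that settles on medication, with the trial dose unchanged.

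- General clause: Grade 3, non-haematologic, not on the exceptions list, so a DLT.
- Hypertension criterion: neither uncontrolled nor requiring dose reduction, so not a DLT.
- Because any one criterion suffices, the literal result is a DLT. The hypertension criterion then does nothing for events of Grade 3 or above.

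This needs no outside grading threshold, since the general clause works on grade alone.

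**NOTE.** Apply it literally to each laboratory-based criterion after the value recovers:

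| Criterion in 4.1.7 | By the list | By the NOTE | Settled elsewhere? |
|---|---|---|---|
| Grade 4 or higher AST/ALT, whatever the duration | DLT | not a DLT | no |
| Combined AST/ALT and bilirubin | DLT | not a DLT | no |
| Grade 3 or higher proteinuria | DLT | not a DLT | no |
| Grade 4 thrombocytopenia; Grade 4 anaemia | DLT | not a DLT | no |
| Other Grade 4 laboratory AE | DLT | not a DLT | no |
| Grade 4 neutropenia over 7 days | DLT | not a DLT | 5.2.4 counts it |
| Grade 3 electrolyte abnormality of 72 hours or more | DLT (general clause) | not a DLT | 5.2.4 counts it |

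The Grade 3 or 4 amylase/lipase exception also overlaps with the Grade 4 or 5 criterion, but that is editorial.

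**Can one reclassified patient change the dose?** These are the protocol's own figures (Tables 10.5.1:1 and 10.5.2:1). The EWOC limit is an overdose probability below 0.25. Each cell gives the overdose probability at the current dose and the next recommended dose.

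| State | 0/3 DLT | 1/3 DLT | 2/3 DLT |
|---|---|---|---|
| Part I, 360 mg | 0.005, 720 | 0.052, 720 | 0.241, 360 |
| Part I, 720 mg after 0/3 at 360 mg | 0.016, 720 | 0.093, 720 | 0.319, 360 |
| Part II, 120/240 | 0.054, 360/240 | 0.228, 120/240 | 0.528, none |
| Part II, 360/240 after 0/3 at 120/240 | 0.085, 360/240 | 0.295, 120/240 | 0.602, 120/240 |

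In Part I a first DLT changes nothing and a second in the same cohort does. In Part II a first DLT already changes the dose, but that table rests on dummy data.

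**Check of the Part I model.** Inputs: logit(p) = log(α) + β·log(d/720), with the mixture prior of Table 7.1.1:2, integrated on a grid and updated with binomial likelihoods.

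- Prior probabilities of under, target and overdose: 0.923/0.050/0.027 at 360 mg (Table 7.1.1:3 gives 0.925/0.049/0.026) and 0.749/0.171/0.081 at 720 mg (0.751/0.169/0.080).
- Overdose probability at 720 mg after 0/3 at 360 mg, for 0, 1 and 2 DLTs in 3: 0.007, 0.055 and 0.332 (table: 0.016, 0.093, 0.319). All fall on the same side of 0.25 as the table.
- After 2/3 at 360 mg the recomputed value is 0.386 against 0.241. This row does not reproduce, though both values rule out escalation to 720 mg.
- The printed Part II prior gives an overdose probability of 0.423 at 120/240 against 0.187 in Table 7.1.2:6, so Part II is taken from the protocol's table alone.

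**How often could the hypertension question arise?** No cycle-1 rate is given. For an assumed rate q of controlled Grade 3 hypertension in cycle 1, the chance of at least one case in a cohort of 3 is 1 − (1 − q)³: 14.3% at q = 5%, 27.1% at 10%, and 62.0% at 27.6%. The last uses the any-cycle figure only as the upper end of the range. These are chances that the ambiguity arises, not effects on the MTD.

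**The case against.** A specific criterion normally overrides a general one, and the context favours that reading for hypertension. Section 4.1.6 bars retreatment only while hypertension is uncontrolled and attaches no dose cut to controlled hypertension. The criterion's own condition about dose reduction would be idle if every Grade 3 episode were already a DLT. Section 1.4.2 treats hypertension as an expected class effect, and 5.2.9.1.4 lists severe hypertension as an AESI separate from DLTs. Every potential DLT is reviewed jointly. The SMC sees all Grade 2 or higher cycle-1 toxicity, decides the dose, and may declare any dose meeting EWOC as RP2D. For the NOTE, a reader may suppose that it covers only laboratory changes not named in the list.

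This is good evidence of intent and limits the consequence. It does not supply the missing rule. Control by medication is not a stated ground for setting an event aside on review. Amendment 1 shows the sponsor handling controllability through the exceptions list: it removed the exception for controllable Grade 3 infusion reactions. The NOTE is worded for any laboratory abnormality and contains no carve-out for named criteria.

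Three stronger readings are tempting and not supported.

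- That counting controlled hypertension would sharply lower the chance of declaring 720 mg. This needs the 27.6% to be a cycle-1 rate at that dose. It is an any-cycle figure not tied to a dose, and SMC discretion cannot be modelled.
- That one patient always moves the dose. The 0/3 to 1/3 states in Part I show otherwise.
- That the Part I prior was built on a different rule. The 27.6% equals 8/29, and 29 patients were treated in trial 1336-0001, whose only DLT among 28 evaluable patients was a pulmonary embolism. Neither the timing of the episodes nor that trial's DLT definition is given, so this is a question for the sponsor.

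**Conclusion.** The contradiction stands on the text alone. Controlled Grade 3 hypertension has two opposite classifications, with the specific criterion the likelier intent. The NOTE, followed as written, removes recovered events under every laboratory-based criterion from the primary count; intent to the contrary is documented only for the 7-day and 72-hour rules.

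The size is conditional: one reclassified patient changes the next recommended dose in some states of the protocol's tables and not in others. No change in the probability of declaring any dose is claimed for hypertension, and no effect size for the NOTE. The dose statements assume that the SMC follows the model, which only guides it. This should be fixed, because the rule defines the primary endpoint and the repair is short.

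**What to change.** In Protocol 4.1.7:

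1. Add to the exceptions of the general clause: *Grade 3 hypertension that does not meet the hypertension criterion below; all other DLT criteria, including the >14-day delay criterion, still apply.* The second half matters: sending hypertension only to its own criterion would drop a patient whose Cycle 2 is delayed by more than 14 days.
2. Add to the NOTE: *This NOTE does not exempt an event that meets a separately listed criterion (the haematologic criteria, combined AST/ALT and bilirubin, Grade 4 AST/ALT, Grade ≥3 proteinuria, any Grade 4 or 5 AE under the non-haematological heading apart from the amylase/lipase exception) or a Grade 3 electrolyte abnormality lasting 72 hours or more.* Transient isolated Grade 3 laboratory changes stay exempt. Naming the heading keeps the 7-day limit for neutropenia intact.

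Ask the sponsor to confirm the intended hypertension rule, and which rule produced the DLT counts in Table 7.1.1:1.

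Cost: the changes need an amendment with IRB/IEC and authority approval (8.1) and can go with the next planned one. A few recovered Grade 4 laboratory events will count as DLTs. Patients already treated need re-checking only if they had Grade 3 hypertension or a recovered laboratory criterion. No extra patients or assessments are needed.

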Trial endpoints	Part I (monotherapy part) Primary: 
- Maximum tolerated dose (MTD).- Number of patients with DLTs in the MTD evaluation period. Secondary: 
- PK parameters of BI 836880: C_{max} and area under the curve (AUC)_{0-504h} Part II (combination therapy part) Primary: 
- Maximum tolerated dose (MTD).- Number of patients with DLTs in the MTD evaluation period.

	Secondary: - PK parameters of BI 836880 and of BI 754091: C_{max} and AUC_{0-504h}
Trial design	Open label, uncontrolled, non-randomised, dose-escalation design
Total number of patients treated	Approximately 24
Number of patients on each treatment	Approximately 24
Diagnosis	Patients with a confirmed diagnosis of advanced, unresectable, and/or metastatic solid tumours
Main in- and exclusion criteria	
Main inclusion criteria:
 
Patients with a confirmed diagnosis of advanced, unresectable, and/or metastatic solid tumours (any type)Patients with no therapy of proven efficacy, or who are not amenable to standard therapiesEastern Cooperative Oncology Group (ECOG) performance status ≤ 1Adequate organ function defined with laboratory values 
Main exclusion criteria:
 
Known hypersensitivity to the trial drugs or their excipientsKnown HIV, HBV, or HCV infectionHistory of severe hypersensitivity reactions to other mAbsSignificant cardiovascular/cerebrovascular diseases, or uncontrolled hypertensionHistory of severe haemorrhagic or thromboembolic events in the past 12 monthsPatients who require full-dose anticoagulationUntreated brain metastasis(es) that may be considered activeHaematological malignanciesHistory (including current) of interstitial lung disease or pneumonitis within the last 5 yearsImmunosuppressive corticosteroid doses (>10 mg prednisone daily or equivalent) within 4 weeks prior to the first dose of trial medication
Test product(s)	BI 836880 BI 754091 (Part 2 only)
dose	
Part 1: BI 836880: starting dose 360 mg every three weeks
 
Part 2: BI 836880: starting dose 120 mg every three weeks BI 754091: starting dose 240 mg every three weeks The starting dose of BI 836880 may be adapted via protocol amendment based on the most recent safety information from another ongoing trial, 1336-0011.

mode of administration	Intravenous infusion

Comparator product(s)	Not applicable
dose	Not applicable

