4.1.8 Definition of evaluable patient

For decisions on dose escalation, an evaluable patient is defined as a patient who has received BI 836880 or BI 836880 plus BI 754091 and either:

- has completed cycle 1 without experiencing DLT

OR

- has experienced DLT during cycle 1

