5.2.9.1.4 Adverse events of special interest

The term adverse events of special interest (AESI) relates to any specific AE that has been identified at the project level as being of particular concern for prospective safety monitoring and safety assessment within this trial, e.g. the potential for AEs based on knowledge from other compounds in the same class. AESIs need to be reported to the sponsor’s Pharmacovigilance Department within the same timeframe that applies to SAEs, please see Section [5.2.9.2.2](#).

In this trial, dose limiting toxicities, severe hypertension, immune-related adverse events, infusion-related reactions, and hepatic injury are considered as AESIs.

Dose limiting toxicities

All DLTs are considered to be AESIs, and must be reported as such. The definition of DLT is presented in Section [4.1.7](#).

Severe hypertension

A hypertensive episode will be considered an AESI if:

- Systolic blood pressure ≥ 140 mmHg or diastolic blood pressure ≥ 90 mmHg which persist longer than 2 days despite either initiation of antihypertensive agent(s) in a patient without prior history of hypertension, or intensification / addition of new antihypertensive agents in a patient with prior history of hypertension.

Immune-related adverse events (irAEs) (Part II only)

Proprietary confidential information © 2019 Boehringer Ingelheim International GmbH or one or more of its affiliated companies

Immune-related AEs are AEs associated with immunotherapy treatments that appear to be associated with the immune therapy's mechanism of action, such as BI 754091 in this study. These adverse reactions, which can be severe, may involve the gastrointestinal, skin, liver, endocrine, respiratory, renal, or other organ systems. The sponsor has defined a list of potential irAEs that could occur with BI 754091 (Appendix [10.1](#)). These irAEs must be reported as AESIs. If an Investigator determines another event (not on the list) should be a potential irAE, the Investigator may also report that event as an AESI.

Recommendations for the management of irAEs are presented in Appendix [10.2](#).

Infusion-related reactions

In the event of an infusion-related reaction \leq Grade 2, the infusion should be temporarily stopped. Upon recovery, it should be infused at 50% of the initial rate until completion of the infusion. In patients experiencing infusion-related reactions \leq Grade 2, subsequent infusions may be administered at 50% of the initial rate.

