10. APPENDICES

10.1 IMMUNE-RELATED ADVERSE EVENTS OF SPECIAL INTEREST

Table 10.1: 1 Immune-related adverse events of special interest

This table defines immune-related AEs that must be reported as AESIs if they occur after exposure to BI 754091.

Immune-related adverse events of special interest
Pneumonitis (report as AESI if an irAE is \geq Grade 2)

• Acute interstitial pneumonitis• Interstitial lung disease• Pneumonitis
Colitis (report as AESI if an irAE is \geq Grade 2 or any grade resulting in dose modification or use of systemic steroids to treat the AE)

• Intestinal obstruction• Colitis• Colitis microscopic• Enterocolitis• Enterocolitis haemorrhagic• Gastrointestinal perforation• Necrotizing colitis• Diarrhea
Endocrine (report as AESI if an irAE is \geq Grade 3 or \geq Grade 2 and resulting in dose modification or use of systemic steroids to treat the AE)

• Adrenal insufficiency• Hyperthyroidism• Hypophysitis• Hypopituitarism• Hypothyroidism• Thyroid disorder• Thyroiditis• Hyperglycaemia, if \geq Grade 3 and associated with ketosis or metabolic acidosis
Endocrine (report as AESI for any grade)

• Type 1 diabetes mellitus (if new onset)

Immune-related adverse events of special interest

Hematologic (report as AESI if an irAE is \geq Grade 3 or any grade resulting in dose modification or use of systemic steroids to treat the AE)

- Autoimmune haemolytic anaemia
- Aplastic anaemia
- Thrombotic thrombocytopenic purpura
- Idiopathic (or immune) thrombocytopenia purpura
- Disseminated intravascular coagulation
- Haemolytic-uraemic syndrome
- Any Grade 4 anaemia regardless of underlying mechanism

Hepatic (report as AESI if an irAE is \geq Grade 2, or any grade resulting in dose modification or use of systemic steroids to treat the AE)

- Hepatitis
- Autoimmune hepatitis
- Transaminase elevations (ALT and/or AST)

Infusion Reactions (report as AESI for any grade)

- Allergic reaction
- Anaphylaxis
- Cytokine release syndrome
- Serum sickness
- Infusion reactions
- Infusion-like reactions

Neurologic (report as AESI for any grade)

- Autoimmune neuropathy
- Guillain-Barre syndrome
- Demyelinating polyneuropathy
- Myasthenic syndrome

Ocular (report as AESI if an irAE is \geq Grade 2 or any grade resulting in dose modification or use of systemic steroids to treat the AE)

- Uveitis
- Iritis

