10.2 MANAGEMENT OF IMMUNE-RELATED ADVERSE EVENTS (PART II ONLY)

Management of immune-related adverse event toxicities associated with anti-PD-1 mAbs are presented below. **BI 754091 should be permanently discontinued for Grade 3-4 pneumonitis, Grade 3-4 adrenal insufficiency, Grade 4 diabetes mellitus, any grade encephalitis, Grade 4 hypophysitis, Grade 4 rash, Grade 3-4 or recurrent colitis of any grade, any recurrent Grade 3-4 AE, transaminase increased >5 times ULN or total bilirubin >3 times ULN (unless unequivocally attributable to another cause), inability to taper steroids to 10 mg or less prednisone or equivalent within 12 weeks, or persistent Grade 2-3 AEs that do not recover to Grade 1 or less within 12 weeks.**

- Pneumonitis:
 - For Grade 2 events, treat with systemic corticosteroids. When symptoms improve to Grade 1 or less, steroid taper should be started and continued over no less than 28 days.
 - Add prophylactic antibiotics for opportunistic infections in the case of prolonged steroid administration.
 - For Grade 3-4 events immediately treat with i.v. steroids. Administer additional anti-inflammatory measures, as needed.
 - BI 754091 should be permanently discontinued for Grade 3-4 pneumonitis, inability to taper steroids to 10 mg or less prednisone or equivalent within 12 weeks, or persistent Grade 2 AEs that do not recover to Grade 1 or less within 12 weeks.
- Diarrhoea/Colitis:

Subjects should be carefully monitored for signs and symptoms of enterocolitis (such as diarrhoea, abdominal pain, blood or mucus in stool, with or without fever) and of bowel perforation (such as peritoneal signs and ileus).

 - All subjects who experience diarrhoea/colitis should be advised to drink liberal quantities of clear fluids. If sufficient oral fluid intake is not feasible, fluid and electrolytes should be substituted via i.v. infusion. For Grade 2 or higher diarrhoea, consider GI consultation and endoscopy to confirm or rule out colitis.
 - For Grade 2 diarrhoea/colitis that persists greater than 3 days, administer oral corticosteroids.
 - For Grade 3 or 4 diarrhoea that persists >1 week, treat with i.v. steroids followed by high-dose oral steroids.
 - For Grade 3 or 4 colitis, or recurrent colitis of any grade, permanently discontinue BI 754091, and immediately treat with i.v. steroids followed by high-dose oral steroids.
 - When symptoms improve to Grade 1 or less, steroid taper should be started and continued over no less than 28 days.

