The frequency of patients with adverse events will be summarized by highest CTC grade (grades 1, 2, 3, 4, 5 and all grades), treatment, primary system organ class and preferred term for each of the following AE tables as well as relatedness of AEs to treatment and seriousness:

For Part I and Part II:

- All AEs
- Drug-related AEs
- AEs leading to dose reduction
- Drug-related AE leading to dose reduction
- AEs leading to treatment discontinuation
- Drug-related AEs leading to treatment discontinuation
- Drug-related AEs leading to treatment discontinuation or dose reduction

- AEs leading to death
- Serious AEs
- Drug-related serious AEs
- Non-serious AE with higher than 5% occurrence rate
- Adverse Events of Special Interest (AESIs)
- DLTs

Part II only:

- Immune-related AEs
- Immune-related AEs leading to dose reduction
- Immune-related AEs leading to treatment discontinuation
- Immune-related AEs leading to treatment discontinuation or dose reduction

All tables will be sorted by system organ classes (SOC) according to the standard sort order specified by the European Medicines Agency (EMA). Preferred terms (PTs) will be sorted by frequency (within SOC).

The above tables will be repeated with the project defined grouping of AE terms. Details of the project defined groupings are defined in the technical TSAP. In these tables the grouped AEs will replace the original PTs for all AEs that are included within the grouped term. The grouped AE categories will then be tabulated along with all remaining MedDRA PTs, sorted by descending frequency.

A reference table presenting the entire project defined groupings and MedDRA PTs within each grouping will also be produced.

Additional AE tables will be produced for AEs of special interest (hepatic injury as defined in CTP Section 5.2.9.1.4 and dose limiting toxicities as defined by 4.1.7), providing further details on highest CTC grade, action taken with study drug and time to first onset of AE.

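### Protocol 4.1.7 ties the BLRM re-run for late immune-related DLTs to Part 1 (monotherapy), although BI 754091 and irAEs belong to Part II

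*Protocol*

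**What the plan says.** Protocol 4.1.7 gives the definition: "Late immune-related DLTs are irAEs that meet the same grading criteria as DLT criteria, but occur after Cycle 1 administration during Part 1". The rule that uses the term follows: "If any late immune-related DLT is reported during dose-escalation, the BLRM will be rerun including the late immune-related DLT". The updated results then go to the SMC, which recommends the next dose level and cohort size.

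Other places fix where BI 754091 and immune-related events belong:

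- Protocol 3.1 makes Part I the monotherapy part and Part II the combination part. Both are dose escalation.
- The synopsis lists "BI 754091 (Part 2 only" among the test products.
- Protocol 5.2.9.1.4 heads its reporting rule "Immune-related adverse events (irAEs) (Part II only".
- Protocol 10.1 opens with "This table defines immune-related AEs that must be reported as AESIs if they occur after exposure to BI 754091".
- Protocol 10.2 is titled "MANAGEMENT OF IMMUNE-RELATED ADVERSE EVENTS (PART II ONLY".
- SAP 7.8.1 places the irAE tables, for example "Immune-related AEs leading to dose reduction", under a Part II only list.

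**The concern.** The definition names the part in which the checkpoint inhibitor is not given and leaves out the part in which it is. The re-run sentence names no part itself, but it is triggered by the defined term and so inherits the limit to Part 1.

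At stake is one safeguard. Late immune toxicity in Part II might reach the SMC without updated model results when the next combination dose and cohort size are chosen.

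**Working it through.** **Step 1: what Part 1 means.** The protocol uses Arabic and Roman numerals for the same two parts. Section 7.1.2 lists Part 1 of this study as a source of BI 836880 monotherapy data, so the phrase cannot refer to another trial. It cannot stand for dose escalation in general either, because both parts escalate.

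**Step 2: does another passage supply the same run in Part II?**

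| Place | What happens to a late event | Model re-run before the next cohort required? |
|---|---|---|
| 4.1.3 | SMC discusses data beyond cycle 1 | No |
| 3.1 | De-escalation possible on overall safety data | No |
| 4.1.4, 4.1.5 | Non-DLT AEs and AEs after the MTD evaluation period are weighed | No |
| 4.1.7, 5.2 | DLTs of all cycles considered for the RP2D, with a BLRM run | Only for the recommended dose |
| SAP 7.4 | DLTs in any cycle tabulated; BLRM on the MTD evaluation period | No |

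The gap is therefore the additional run between Part II cohorts, and nothing wider.

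**Step 3: can one counted DLT change the recommendation?** Table 10.5.2: 1 answers this without recomputation. The limit is P(overdose) below 0.25. I assume that the re-run counts the late event as a DLT at the dose the patient received. P(OD) below is for the current dose.

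| Scenarios | One more DLT | P(OD) | Next dose |
|---|---|---|---|
| 4 to 5 | 0/3 to 1/3 at 360/240, after 0/3 at 120/240 | 0.085 to 0.295 | 360/240 to 120/240 |
| 2 to 3 | 1/3 to 2/3 at 120/240 | 0.228 to 0.528 | 120/240 to none |
| 5 to 6 | 1/3 to 2/3 at 360/240, after 0/3 at 120/240 | 0.295 to 0.602 | 120/240 both times |

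The first two pairs change the recommendation and the third does not. I do not rely on scenarios 1 and 2. The recommendation of 360/240 in scenario 1 has P(overdose) 0.248, too close to 0.25 to carry weight.

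**Step 4: a side check with more patients at 360/240.** I used the 7.1.2 model:

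- odds(π12) = odds(π1 + π2 − π1π2) × exp(η × d1/500 × d2/240)
- posterior proportional to prior × Π π^r (1 − π)^(n − r)

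With the compound 1 and compound 2 rows of Table 7.1.2: 5 as printed, prior P(overdose) at 120, 360, 500 and 720 mg is 0.422, 0.593, 0.651 and 0.701. This does not match Table 7.1.2: 6 (0.187, 0.409, 0.653, 0.822). With the rows exchanged it is 0.185, 0.404, 0.651 and 0.823, which does. That suspected row swap is a separate matter.

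After 0/3 at 120/240, moving from 0/6 to 1/6 at 360/240 takes P(overdose) there from 0.027 to 0.121 with rows exchanged, and from 0.048 to 0.172 as printed. Under either order 360/240 stays within the limit.

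**The case against.** The strongest reply is that nobody would be misled. The re-run sentence speaks of dose escalation, which covers both parts, and a trial team would probably apply it in Part II. Nothing bars the SMC from asking for a run, and its charter, which is not among these documents, may provide for one. Section 7.1.2 adds that Part 2 BLRM calculations will use all available information. Most of this stands as mitigation. It does not close the gap: the 7.1.2 sentence concerns the prior, and an escalation trigger should not depend on readers setting aside its own definition.

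The second reply is that the effect is limited. That also stands. The 0/3 to 1/3 case needs the late event to arrive before more DLT-free patients are evaluable at 360/240. After three more, the comparison is 0/6 to 1/6, and 360/240 remains admissible.

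A reader might also infer a conflict with 4.1.8, because the patient concerned "has completed cycle 1 without experiencing DLT". The documents do not support that. Section 4.1.8 decides who is evaluable, so the patient stays in n. Section 7.1.2 counts DLTs out of n patients. Including the late event therefore turns 0/3 into 1/3, and no exception to 4.1.8 is needed.

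**Conclusion.** The point holds as a scope error in an operative escalation rule, probably a drafting slip. On a literal reading, the re-run in 4.1.7 is not triggered by late irAEs in Part II, and no other passage requires it there. It should be corrected, at the lower end of that category.

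One event can move the model's recommendation from 360/240 to 120/240 (P(overdose) 0.085 against 0.295), but not in every constellation. In that pair, omitting the event means staying at the current dose, not moving higher. The figures are illustrative, because the Part II prior rests partly on dummy data that 7.1.2 says will be replaced.

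Two stronger readings are tempting, and the documents support neither. Late Part II immune toxicity is not ignored: the SMC reviews it, and it counts towards the RP2D. Nor is the MTD estimate or the overdose criterion biased. Both are defined on cycle 1 DLTs (protocol 2.1.1.1, 4.1.7, 7.3.2; SAP 7.4), and the wording on late events does not touch them.

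**What to change.** Reconcile the part named in protocol 4.1.7 with the synopsis, 5.2.9.1.4 and 10.2, so that the definition and the BLRM re-run cover Part II. State whether they also apply in Part I. Keep the SMC review, and leave the MTD analysis on cycle 1 DLTs.

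Optionally, the sponsor may confirm that in this re-run the patient stays in n and is counted once, as a DLT.

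The cost is one corrected phrase and a short statement of scope in 4.1.7, with no SAP change. The downside is an occasional extra BLRM run and possibly slower escalation.
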